Patients admitted to the hospital and who undergo cardiac catheterization for an AMI will be identified through the electronic medical record (EMR). Those with a diagnosis of COPD in the EMR will be offered participation in the study. Baseline characterization will include demographics, smoking history, prior history of exacerbations in the year before admission, supplemental oxygen use, respiratory and cardiac medication use, comorbidities including history of coronary artery disease, heart failure and ejection fraction, and pulmonary function data as available in the EMR. Results of this Aim will provide data about the prevalence and clinical characteristics of COPD in the hospitalized population with AMI in our network. The Aim will also provide an estimate of the number of annual admissions for patients with COPD and AMI.

Specific Aim 2. To determine the association between beta-blocker use at discharge and cardiopulmonary outcomes in patients with COPD and AMI.

Patients with AMI and EMR-documented COPD will be followed, prospectively from the time of discharge using review of the electronic medical record and as local guidance permits, phone calls at 3 and 6 months. We will determine the associations between beta-blocker use at discharge and the risk for all-cause mortality, recurrent ischemic events, and hospitalization for COPD exacerbation adjusting for baseline characteristics and COPD severity.

4. Study Design and Methods

- a) **Overview.** The study is a prospective, observational study of patients admitted to the BLOCK COPD network hospitals with acute AMI and COPD. Patients with will be identified via the EMR. Because of the current COVID-19 pandemic and the possibility of limited access to hospitalized patients, the study consists of three options for enrollment. Option 1 or 2 is preferable if local guidance permits.

Option 1: A total of 3 visits including 1 in person visit in the hospital and 2 follow up phone calls with EMR review at 3 and 6 months after discharge. Sites may consider alternatives to in person consent and data collection including by telephone or video conference.

Option 2: EMR review at the time of hospital admission followed by post-discharge telephone consent and 2 follow up phone calls with EMR review at 3 and 6 months.

Option 3: EMR review at the time of hospital admission and follow-up review of the EMR at 3 and 6 months after discharge.

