 - iii. COPD assessment - year of diagnosis, home use of supplemental oxygen, self-reported history of spirometry being conducted, number of hospitalizations for COPD exacerbations in the year prior to admission, number of courses of antibiotics and/or steroids for COPD exacerbations in the year prior to admission. For protocol Option 1 this will be collected via self-report utilizing a questionnaire during the hospitalization. For protocol Option 2, this information will be obtained

after discharge and phone consent. For protocol Option 3 as much of this information as possible will be collected from review of the EMR.

- iv. Most recent forced expiratory volume (FEV1) and forced vital capacity (absolute and percent predicted) from EMR if documented in the 3 years prior to admission
- v. Comorbidity assessment to include cardiovascular disease and risk: history of hypertension, hyperlipidemia, coronary artery disease, prior MI, heart failure (ejection fraction prior to admission if available), percutaneous coronary intervention (PCI), coronary artery bypass grafting (CABG), peripheral vascular disease, stroke, diabetes mellitus, cirrhosis, asthma, obstructive sleep apnea, depression, anxiety, end-stage renal disease, cancer (type), organ transplantation (type)
- vi. Respiratory medication use on admission
- vii. Cardiovascular medication use on admission
- viii. Assessment of in hospital MI treatment: thrombolytics, PCI, CABG
- ix. Diagnosis of ST elevation MI (STEMI) or non-ST elevation MI (NSTEMI)
 - x. Initial post MI ejection fraction from inpatient echocardiogram
 - xi. Length of hospital stay
 - xii. Length of ICU stay
 - xiii. Need for intubation
 - xiv. Cardiogenic shock during hospital stay
 - xv. Discharge cardiovascular medications
 - xvi. Discharge disposition
- b. Phone calls (Option 1 only) and EMR review at 3 and 6 months
 - i. Vital status
 - ii. Date and cause of death if applicable
 - iii. Interval history of hospitalization and primary diagnosis (all events will be captured but hospitalizations for COPD exacerbations, recurrent MI, revascularization, or heart failure will be specifically queried)
 - iv. Interval history of treatment with steroids or antibiotics for exacerbations of COPD
 - v. Beta-blocker use and reason for discontinuation, if applicable Medical records will be collected for all admissions

g) Analytic and Statistical considerations.

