- a. Analysis plan for Aim 1. The primary objectives of Aim 1 are to determine the number of admissions per year for AMI at our participating institutions and the prevalence of COPD in that population. These prevalence estimates will be calculated as a simple fraction. We will also compare the clinical characteristics of COPD patients discharged on a beta-blocker versus those not discharged on a beta-blocker using t-tests or chi-square tests (or Fisher's exact tests) as appropriate.
- b. Analysis plan for Aim 2. For the primary analysis we will compare the risk of death or all-cause hospitalization at 6 months for patients with AMI and COPD who were discharged alive on beta-blockers to that of patients not

discharged on beta-blockers. Secondary analyses will include comparisons of rates of hospitalization for COPD exacerbations, rates of hospitalization for recurrent MI or revascularization or heart failure, and rates of treatment with steroids and/or antibiotics for exacerbations. The primary analysis will be based on adjusted Kaplan–Meier survival curves that describe the probability remaining alive and out of hospital in those discharged versus not discharged on beta-blockers, while adjusting for the inverse probability of treatment weighting (IPTW) to reduce confounding. For all time-to-event analyses, the start time will be when the participant is discharged from the hospital.

Participants will be censored at 6 months post-discharge if no event occurred. The comparison of clinical characteristics between treatment groups conducted in aim 1 will be used to inform the calculation of the IPTW. We will use the adjusted log-rank test to compare the two curves. As secondary analyses, we will use both IPTW and adjusted Cox proportional-hazards models to assess the association between the beta-blocker prescription and death or re-hospitalization. Adjusted models will also include the covariates of race, sex, baseline age, smoking status, number of hospitalizations for COPD during the previous year, use of supplemental oxygen, presence of ejection fraction <40% at discharge. Assuming adequate frequencies between groups, we will stratify the models by beta-blocker use at the time of admission, presence of asthma, STEMI vs. NSTEMI, and site. Rates of exacerbation will be analyzed by IPTW negative binomial regression models and will be used to compare annualized rates of hospitalization.

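### No listed item covers COPD exacerbations treated during the index stay or courses continuing at discharge, so the secondary steroid/antibiotic rate may include courses begun before discharge

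*Combined protocol and SAP*

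**What the plan says.** The plan records exacerbation treatment in two windows.

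- **Before admission.** Section 4.f.a, item iii, takes the "number of courses of antibiotics and/or steroids for COPD exacerbations in the year prior to admission".
- **After discharge.** Section 4.f.b, item iv, takes "Interval history of treatment with steroids or antibiotics for exacerbations of COPD" at 3 and 6 months. Under Aim 2 in section 3, patients "will be followed, prospectively from the time of discharge using review of the electronic medical record".

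For drugs, section 4.f.a lists "Respiratory medication use on admission" (item vi) and "Discharge cardiovascular medications" (item xv). The nearest respiratory item for the stay itself is intubation.

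Section 4.g.b names "rates of treatment with steroids and/or antibiotics for exacerbations" among the secondary comparisons. On the time origin it says: "For all time-to-event analyses, the start time will be when the participant is discharged from the hospital". On the rate model it says: "Rates of exacerbation will be analyzed by IPTW negative binomial regression models and will be used to compare annualized rates of hospitalization". That sentence states no time origin and does not say what counts as a new course. Section 4.g.b also says that the Aim 1 comparison of baseline characteristics will guide the inverse probability of treatment weights (IPTW).

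**The concern.** The index stay falls between the two windows. Take a patient whose COPD flared during the infarction admission and who went home part-way through a steroid or antibiotic course. That patient has, truthfully, been treated for an exacerbation since discharge. No listed field shows that the course began earlier, and no counting rule tells the site or the analyst what to do with it.

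The timing matters because exposure is defined by the discharge prescription. An exacerbation during the stay comes before that decision and may influence it: section 2 says that COPD patients are often denied beta-blockers over worries about lung function. If so, an event that helped determine exposure could be scored as an outcome of exposure. It would also be a confounder that cannot enter the weights, because it is not a listed item.

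At stake is the credibility of one secondary respiratory comparison. Section 3 gives COPD outcomes a place in Aim 2, and section 2 criticizes earlier studies for thin pulmonary follow-up.

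**Working it through.** **Step 1: is there a plan figure to reproduce?** Not for this endpoint. Table 1 and the recruitment figures (500 discharged alive; 500 / (1 − 0.125) = 571.4, stated as 571) concern death or all-cause hospitalization. They do not bear on this point, except that 500 is used in step 5.

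**Step 2: set the listed items against what is needed.**

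| Needed to separate old from new courses | Listed in 4.f or 4.g? |
|---|---|
| Exacerbation treated during the index stay | No |
| Steroid or antibiotic course ongoing at discharge | No |
| Respiratory drugs at discharge | No (admission only) |
| Start date of each course reported at follow-up | No |
| Rule for a course already running at discharge | No |
| Time origin for the rate model | Not stated (discharge is stated for time-to-event analyses) |

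**Step 3: formula for the bias.** The documents give none of the following inputs, so all are assumptions:

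- λ = truly new courses per patient in 6 months, equal in both groups (no true effect)
- q1, q0 = shares of patients discharged on and off beta-blockers whose in-hospital course is counted after discharge, one course each
- equal follow-up and no weighting

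Observed rate ratio = (λ + q1) / (λ + q0).

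**Step 4: results with no true effect.**

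| q1 vs q0 | λ = 0.3 | λ = 0.5 | λ = 1.0 |
|---|---|---|---|
| 5% vs 5% | 1.00 | 1.00 | 1.00 |
| 5% vs 10% | 0.875 | 0.917 | 0.955 |
| 5% vs 15% | 0.778 | 0.846 | 0.913 |
| 5% vs 20% | 0.700 | 0.786 | 0.875 |
| 10% vs 30% | 0.667 | 0.750 | 0.846 |

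Example: (0.5 + 0.05) / (0.5 + 0.10) = 0.55 / 0.60 = 0.917.

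Three further cases, all at λ = 0.5 in the group off beta-blockers:

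- Carry-over reversed (10% on, 5% off): 0.60 / 0.55 = 1.09, which is apparent harm.
- True ratio 1.20, carry-over 8% vs 20%: (0.60 + 0.08) / (0.50 + 0.20) = 0.97, so a real excess is hidden.
- True ratio 0.75, carry-over 5% in both groups: (0.375 + 0.05) / 0.55 = 0.77. At 20% in both: (0.375 + 0.20) / 0.70 = 0.82. Equal carry-over only dilutes a true effect.

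**Step 5: effect on a nominal 5% test.** Take N = 500, λ = 0.5, q1 = 5%, q0 = 15%, so the group means are m1 = 0.55 and m0 = 0.65. With dispersion k and group sizes n1 and n0,

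SE of log rate ratio = √[(1/m1 + k)/n1 + (1/m0 + k)/n0].

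With 85% on beta-blockers (n1 = 425, n0 = 75) and k = 0.5, SE = √[(1.818 + 0.5)/425 + (1.538 + 0.5)/75] = 0.181. The log ratio is ln(0.55/0.65) = −0.167, which is 0.92 standard errors. The rejection probability is about 15%. With k from 0.5 to 1.0 it is about 13–15% at an 85% beta-blocker share and 21–24% at a 45% share, against the nominal 5%.

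**The case against.** The strongest reply is that the plan is silent rather than wrong. It never says that in-hospital courses are counted, and an interval history taken from discharge is naturally read as exacerbations arising in that interval. Every follow-up contact is paired with EMR review, sites already abstract the index chart, and section 4.f.b says medical records will be collected for all admissions. Aim 1 in section 3 mentions respiratory medication at baseline without limiting it to admission. The case report form is not in the documents. So a reader who infers that the plan counts carried-over courses as new, or that the two can never be told apart, goes further than the text. This part stands: such courses may be counted, and the information may exist in the chart. But holding a chart is not the same as having a field to abstract or a rule to apply, and the records sentence sits under the follow-up contacts without naming the index stay.

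The direction is also inferred. Section 2 describes withholding in COPD generally. It does not mention exacerbations during an infarction stay, and the documents give no frequency for them in either group. This stands too: false protection is conditional.

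Weighting is not powerless either. Collected correlates (prior-year courses and COPD hospitalizations, home oxygen, admission respiratory drugs, FEV1, intubation, length of stay) could narrow a group difference in carry-over if they enter the weights. They need not remove it, and the ratios above are unweighted.

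Finally, this endpoint is one secondary analysis and is not named in the Aim 2 statement. That is correct, and it limits the importance of the point.

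**Conclusion.** The point holds as a gap in data collection and in the counting rule. An exacerbation treated during the index stay, and a course continuing at discharge, are not listed items. A carried-over course may therefore enter the steroid/antibiotic rate, and index-stay exacerbation cannot enter the IPTW.

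If carry-over is commoner in patients not discharged on beta-blockers, the ratio is biased toward apparent protection. A modest illustration (λ = 0.5, 5% vs 10%) gives 0.92, and larger assumed gaps give more. These figures show how the mechanism works and do not estimate its size: every input is assumed and no weighting is applied.

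A reader might infer that the primary result is compromised in the same way. It is not: a carried-over drug course adds no event to death or all-cause hospitalization, or to hospitalization for COPD exacerbation. An unrecorded index-stay exacerbation could still confound those comparisons, but that is a separate matter on which the documents allow no figure.

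The change is worth making because analysts could not recover this pre-exposure variable from the listed data.

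**What to change.** - **Section 4.f.a:** add, from the EMR, a yes/no item for a COPD exacerbation treated during the index stay, and any systemic steroid or antibiotic course for COPD ongoing at discharge, with its start and planned end dates.
- **Section 4.f.b:** record the start date of each course reported at 3 and 6 months.
- **Section 4.g.b:** count only courses that start after discharge; state discharge as the time origin of the rate model; add index-stay exacerbation to the IPTW covariates; report a sensitivity analysis excluding patients treated for an index-stay exacerbation.

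The cost is a few more fields abstracted from a chart the sites already review, dates to obtain at follow-up, and slightly fewer counted events. If index-stay exacerbation strongly predicts the discharge prescription, adding it may make the weights more variable, so their distribution should be reported.

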Gottlieb et al. examined the medical records of more than 200,000 patients with MI as part of the Cooperative Cardiovascular Project (CCP) and found that though beta-blocker use was less common in those with underlying COPD (22% vs. 34%), the overall benefit of beta-blockers on mortality was comparable to that observed in those without COPD (Relative Risk (RR) 0.60; 95%CI, 0.57-0.63).(15) However, no information about the severity of the underlying lung disease was available and the possibility that healthier patients received beta-blockers cannot be excluded. A second study examining data from the CCP did stratify patients with COPD based on whether they were receiving beta-agonists or had been treated with oral steroids or admitted for COPD in the year prior to their MI.(24) In that analysis, COPD patients without these characteristics derived the same mortality benefit from beta-blockers as did patients without COPD (RR 0.85; 95%CI, 0.73-1.00) but no benefit was observed in those treated with beta-agonists or treated for acute symptoms in the year prior. A more recent population-based cohort study from the UK of 1063 patients with COPD and MI occurring between 2003 and 2008 found that treatment with beta-blockers in the hospital, or at the time of discharge, was associated with improved survival compared to no beta-blocker treatment(13). Though this analysis adjusted for COPD severity as assessed by treatment, symptoms and exacerbation history, a large number of patients were excluded as beta-blocker treatment was viewed as contraindicated by the treating physician, in some cases due to COPD. This precludes examination of outcomes in this likely more severely affected group.

The results of our proposed observational study would provide more robust and contemporary data regarding the overall risk-benefit of beta-blockers in COPD patients with acute MI and provide preliminary data about the feasibility of recruitment for a subsequent randomized trial.

3. Specific Aims

Specific Aim 1. To determine the prevalence of COPD in patients admitted to the hospital with an acute myocardial infarction (AMI) and to characterize the phenotypic expression and severity of their underlying lung disease.

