b) **Participant selection and eligibility.** Subjects hospitalized and who undergo cardiac catheterization with AMI and have EMR-documented COPD will be eligible for participation. The age, race, gender, smoking status and comorbidities of patients with who undergo cardiac catheterization for AMI but have no EMR-documented diagnosis of COPD will be recorded but no other information will be collected on this population.

c) **Inclusion Criteria**

- a. Willing and able to provide informed consent (applicable for Option 1 and 2 only)
- b. Men and women age 35 or older
- c. Admitted to hospital from the Emergency Department or by hospital to hospital transfer with a primary diagnosis of AMI
- d. Undergo cardiac catheterization for AMI
- e. EMR-documented COPD

d) **Exclusion Criteria**

- a. Cognitive disorder that in the judgment of the investigator impairs understanding of the study objectives or assessments (applicable for Option 1 only)
- b. Vulnerable populations, including prisoners and pregnant women

e) **Consent Process.** Patients admitted and who undergo cardiac catheterization for AMI will be identified via the EMR. If protocol Option 1 is being followed those with EMR-documented COPD will be approached for participation. They will be asked to provide written consent only after the objectives and risks of the study have been fully explained. Surrogate consent will not be permitted. The reasons for patients not being eligible for the study will be recorded. If protocol Option 2 is being followed a waiver of informed consent will be obtained from local IRBs for the initial EMR review and then telephone consent will be obtained after discharge. If Option 3 is being followed a waiver of consent will be obtained.

f) **Study Visit Schedule and Assessments**

- a. In-hospital visit and EMR review. All data elements will be obtained from the EMR except the self-reported COPD assessment which will be obtained during the hospitalization and after informed consent in protocol Option 1 and after discharge and phone consent in protocol option 2.
 - i. Demographics to include age, gender, race and ethnicity, height, weight
 - ii. Smoking status

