- c. Importance of knowledge gained. The results of proposed Aim 1 will provide data about the prevalence and clinical characteristics of COPD in the hospitalized population with MI in our network. The Aim will also provide an estimate of the number of annual admissions for patients with COPD and MI. Aim 2 will provide valuable information about the associations between beta-blocker use at discharge and the risk for all-cause mortality, recurrent ischemic events, and hospitalization for COPD exacerbation adjusting for baseline characteristics and COPD severity. Even though the parent BLOCK-COPD trial strongly indicated that patients with COPD and at risk for exacerbation should not be prescribed beta-blockers in the absence of an established indication for the drugs such as recent myocardial infarction or heart failure, questions remain about their use in the latter populations. The results of our proposed observational study would provide more robust and contemporary data regarding the overall risk-benefit of beta-blockers in COPD patients with acute MI and provide preliminary data about the feasibility of recruitment for a subsequent randomized trial.

References

1. Collaborators GBDCoD. Global, regional, and national age-sex-specific mortality for 282 causes of death in 195 countries and territories, 1980-2017: a systematic analysis for the Global Burden of Disease Study 2017. *Lancet*. 2018;392(10159):1736-88.
5. Westerik JA, Metting El, van Boven JF, Tiersma W, Kocks JW, Schermer TR. Associations between chronic comorbidity and exacerbation risk in primary care patients with COPD. *Respiratory research*. 2017;18(1):31.

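### Aim 1 promises counts and COPD prevalence for all AMI admissions, but the study identifies only patients who are catheterized

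*Combined protocol and SAP*

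**What the plan says.** **Target.** Section 3 words Aim 1 as the prevalence of COPD in patients admitted with AMI. The paragraph beneath it says the results will describe the "prevalence and clinical characteristics of COPD in the hospitalized population with AMI in our network", and adds: "The Aim will also provide an estimate of the number of annual admissions for patients with COPD and AMI". Section 4.g.a makes it the primary objective of Aim 1 to "determine the number of admissions per year for AMI at our participating institutions and the prevalence of COPD in that population", with the prevalence calculated as a simple fraction. Section 7.c says the Aim 1 results will "provide data about the prevalence and clinical characteristics of COPD in the hospitalized population with MI in our network". None of these statements mentions catheterization.

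**Patients identified.** The operational paragraph of Aim 1 in section 3 begins with patients catheterized for AMI, and section 4.e repeats this: "Patients admitted and who undergo cardiac catheterization for AMI will be identified via the EMR". Section 4.c lists catheterization as an inclusion criterion, separate from the criterion that AMI be the primary diagnosis. For the comparison population, section 4.b provides that a few characteristics of patients "who undergo cardiac catheterization for AMI but have no EMR-documented diagnosis of COPD will be recorded", and that nothing else is collected on them.

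**The concern.** The numerator and the denominator of the planned fraction both consist of catheterized patients, while the quantity it is meant to estimate is defined over all AMI admissions. The protocol treats the two groups as different, since a separate catheterization criterion would be redundant if every AMI admission were catheterized.

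These are the stated primary objectives of Aim 1, so the label on the result matters:

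- The prior range of 13 to 25% in section 4.g.c refers to patients admitted with acute MI. Setting the study's figure against it would compare unlike populations.
- Sections 2 and 7.c say the study will inform the feasibility of recruiting to a later randomized trial. Annual counts are a natural input to that judgement, and a reader would take them as all AMI admissions.

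**Working it through.** The protocol gives no figure for Aim 1 (no expected number of admissions, catheterized share or target precision), so there is nothing to reproduce. The check compares the target with what is captured and then illustrates the consequence.

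**1. Target against capture**

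| Quantity | Stated target | Captured as written |
|---|---|---|
| Annual AMI count | all AMI admissions (4.g.a) | catheterized AMI admissions (3, 4.e) |
| Annual COPD plus AMI count | all such admissions (3) | catheterized, with EMR-documented COPD (4.c) |
| Patients without COPD in the denominator | all AMI admissions without COPD | catheterized only (4.b) |
| Estimator | prevalence in the AMI population | simple fraction, no correction (4.g.a) |

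**2. Counts.** Let c be the catheterization rate in the group being counted. The captured count is N × c, so the shortfall is 1 − c. Assumed rates of 95%, 90%, 80% and 70% give shortfalls of 5%, 10%, 20% and 30%. Only the sign follows from the documents: the count is short whenever c < 1.

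**3. Prevalence.** Let p be the prevalence among all AMI admissions and r the catheterization rate with COPD divided by the rate without. Then

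prevalence among catheterized = p·r / (p·r + 1 − p).

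For example, p = 0.13 and r = 0.7 give 0.091 / (0.091 + 0.87) = 0.091 / 0.961 = 9.5%. The values 13% and 25% are the ends of the range in section 4.g.c, used only as inputs. The 20% and all values of r are assumptions.

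| True prevalence | r = 0.7 | r = 0.9 | r = 1.0 | r = 1.1 |
|---|---|---|---|---|
| 13% | 9.5% | 11.9% | 13.0% | 14.1% |
| 20% | 14.9% | 18.4% | 20.0% | 21.6% |
| 25% | 18.9% | 23.1% | 25.0% | 26.8% |

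The error is zero at r = 1 and changes sign there.

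**4. Both effects together, per 1,000 AMI admissions.** Assume p = 0.13, 80% catheterized overall and r = 0.8. The rate without COPD is 0.8 / (0.13 × 0.8 + 0.87) = 0.8 / 0.974 = 0.821, and the rate with COPD is 0.8 × 0.821 = 0.657. The study would count 800 of 1,000 AMI admissions and 85 of 130 with COPD, and would report 85.4 / 800 = 10.7% instead of 13%.

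**The case against.** The strongest reply is that the restriction is disclosed, and in the right place: it opens the operational paragraph of Aim 1, ahead of the promised outputs. The later references to the AMI population could be read as shorthand for the group just defined, which would make this loose wording. That reading is possible, and it is why rewording is enough as a repair. But the aim statement, the analysis objective and the stated conclusions all name the wider population, and a report written from them would too.

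A second reply is that section 4 limits whom the study approaches and records individually, and does not rule out an aggregate count. Section 4.e also says reasons for ineligibility are recorded, so patients without catheterization might appear there. However, that sentence sits in a paragraph whose starting set is already catheterized patients, and section 4.g.a names the AMI count as an objective without giving any other source. If sites do log all AMI admissions, the protocol should say so and use the log.

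A third reply is that no material bias has been shown. That stands: the rates above are assumptions, and the documents anchor neither the overall catheterization rate nor the ratio. It is also true that Aim 1 is descriptive, with no test or decision rule attached. This limits the consequence, but the population attached to the result is still wrong.

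**Conclusion.** The concern holds. Followed as written, Aim 1 would report counts and a prevalence for a population that the study does not enumerate. Two statements need no outside figure: the counts fall short if any AMI patient in the group counted is not catheterized, and the prevalence describes catheterized admissions. It equals the all-AMI prevalence only if catheterization rates with and without COPD are the same. The direction of any difference in prevalence, and the size of both effects, cannot be determined from the documents.

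The mismatch should be corrected because it affects the primary objectives of Aim 1. It does not affect the Aim 2 comparison, the target of 500 patients discharged alive or the planned 571 consents.

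**What to change.** **Preferred.** Restate the aim and its outputs in section 3, the analysis in section 4.g.a and the conclusions in section 7.c as the prevalence of EMR-documented COPD, and annual counts, among AMI admissions undergoing cardiac catheterization. Drop the claim to all AMI admissions. If the age limit (35 or older) and the admission-route criterion also apply to the group screened, name them in the same label. This is wording only; the cost is a narrower conclusion.

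**Alternative, if the wider estimate is wanted.** Obtain from each site aggregate EMR counts of all admissions with AMI as primary diagnosis, cross-classified by EMR-documented COPD (yes/no) and catheterization (yes/no), with the age and admission-route limits stated. Calculate the Aim 1 figures from all AMI admissions and show the catheterized subset separately. The cost is one extra query per site, in a population the current screen does not cover. Approval would have to be confirmed, particularly at Option 1 sites, because section 4.e describes waivers only for Options 2 and 3.

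Neither route changes Aim 2 eligibility, analysis or sample size.
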